Our Primary Outcome is change in the modified Harris Hip Score at 12 months and 24 months. Secondary outcomes include changes in other validated outcomes measures patient satisfaction, and degree of improvement on physical exam. The influence of OA severity (Outerbridge scoring) and location of OA will also be analyzed to determine if they have an effect on the aforementioned outcome measures. Satisfaction will be assessed by an exit questionnaire (See section IV). In addition to gauging satisfaction, this questionnaire will ask subjects how they felt about their participation in the study. (See section IV)

Inclusion and Exclusion Criteria:

Inclusion criteria	Rationale
Age 40 or greater	Higher likelihood of undetectable OA on imaging
Orthopedic surgeon determines symptoms are consistent with a labral tear.	Required for treatment
Availability of hip radiographs and MRI	Needed to assess eligibility and comparison for specific aim 3
Willingness to undergo randomization and ability to understand and sign informed consent document	Ability to understand study and consent willingly

Exclusion criteria	Rationale
Unexpected pathology at the time of arthroscopy	Source of pain less likely to due dysfunction of the labrum and more likely due to aberrant extra-articular biology
Same site surgery	Complex anatomy
Contraindication to surgery or physical therapy	Cannot tolerate either treatment grouping
Alternate form of PT for greater than 6 weeks	Will negatively augment results. May affect recruitment.

Selection and enrollment:

We will enroll 122 consecutive subjects meeting the aforementioned criteria. Subjects will be randomized into conservative or surgical treatment arms. All potential subjects on the clinic schedule of the investigator will be pre-screened for eligibility based on age, clinical assessment, and previous medical history.

All eligible subjects will be approached at an outpatient clinic visit. Those who initially meet inclusion criteria will be introduced to the study and given a research consent form that they have the opportunity to take home and to review.

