1. The study staff will meet regularly with [name] to review study participants and the data that has been collected on them to date. If a subject becomes disqualified or must leave the study for safety concerns, [name] will personally inform them of the situation through the subjects preferred method of contact. [name] will be leading and administering the conservative arm of the study (subjects being treated non-surgically with physical therapy and subjects in the post-operative period receiving rehabilitative physical therapy). She will inform [name] of patient progress and any potential clinically significant events that may warrant further discussion and could ultimately result in the dismissal of a patient from the study.
 - a. As this is a prospective study comparing the gold standard of treatment (labral repair) to a potentially equivalent therapeutic modality, qualifying subjects will never be denied the option to undergo labral repair via hip arthroscopy. The treatment schema allows for subjects in the non-surgical arm (physical therapy alone) to cross over to the surgical treatment group at any time (following physical therapy) from initial enrollment if they wish to do so. Subjects who decide to crossover or are indicated to crossover through the non achievement of advancement criteria will have the PT discontinued at that time point but must wait for official crossover at 6 weeks after initial enrollment. Participants can always decide to leave the study if this is not what they want. The decision to cross over will in no way affect the quality of healthcare current or prior study participants receive. All of this will also be explained to them during the consent.
 - b. We will review all data continuously and should there be a obvious clinical detriment to specific treatment arm such as repeated poor outcomes or worsening function, further investigation will be initiated to determine if this is an isolated occurrence or if there is a significant trend which warrants cessation of study protocol and disenrollment of subjects.
 - i. Stopping rules include a clear difference in morbidity, as measured by interval physical exams and outcomes questionnaires, between treatment groups
 - ii. Any significant mortality possibly linked to study procedures will result in immediate suspension of the study protocol.

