2. A data safety monitoring board (DSMB) or data monitoring committee (DMC) is not required for the purposes of this study because large numbers of subjects will not be used in this investigation, there are no blinded treatment study groups, we are not using multiple clinical sites (all are within Partners network), we are not using high risk interventions (hip arthroscopy has been shown to be a safe option for managing intra-articular and periarthritis pathology of the hip;

physical therapy is low risk), we are not performing a controlled trial in which major morbidity or mortality are considered primary or secondary endpoints.

Adverse Events Reporting and Assessment:

Any protocol deviations and/or adverse events will be systematically documented and reported to the IRB. Adverse Event Reports and/or Case Report Forms will identify study participants by their initials and a unique study participant identifier.:.

Severity grading scale:

Mild: adverse event of little clinical significance

Moderate: adverse event between mild and severe - causing some limitation of usual activities

Severe: adverse event that results in death, is life-threatening, requires or prolongs hospitalization, causes persistent or significant disability/incapacity, represents a significant overdose or breach of protocol, results in congenital anomalies/birth defects or produces cancer, or in the opinion of the investigator, represents other significant hazards or potentially serious harm to the research subject or others.

Attribution scale:

Not related: clearly NOT related to the study

Possible: may be related to the study

Probable: likely related to the study

Definite: clearly related to the study

Unable to assess

Any serious or unexpected adverse events will be reported to the IRB within the required timeframe, using the appropriate forms. The principal investigator will provide an interim report of all adverse events to the IRB at the time of continuing review. Although this proposed project is perceived to be relatively low-risk, the study may be terminated if the frequency of serious or unexpected adverse events is higher than that anticipated. Once this determination is made, a memo will be sent to the IRB explaining the reasons for the determination. For suspended studies, an action plan will be devised which will outline what evidence and/or conditions will be required to terminate or re-initiate the study.

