Reporting Unanticipated Problems including Adverse Events

The principal investigator will report to the PHRC any unanticipated problems and adverse events that occur: 1) during the conduct of the study, 2) after study completion, 3) after subject withdrawal or completion. The reports will be submitted according to PHRC policy within 5 working days or 7 calendar days of the date the investigator first becomes aware of the problem.

Subject Confidentiality:

Precautions will be taken when contacting and communicating with subjects to ensure that their participation is kept confidential. Subjects will be assured that their decision to participate will not affect their medical treatment. Throughout the study, investigators will be alert to any complaints or adverse reactions and will take appropriate steps to alleviate the difficulties as soon as possible. Subjects will be given the names and phone numbers of individuals to contact in the event of an emergency or a complaint or question regarding the conduct of the study.

All data for presentation will be identified by a code number only. Prior to releasing data to the scientific community, all data will be de-identified. Explicit permission to share the de-identified data with the scientific community will be obtained as part of the Informed Consent procedures.

Safeguarding Specimens, Records, and Data:

All research materials are obtained directly from the participants by trained and supervised study staff. All study staff who interact with human subjects have completed the requisite training in research ethics and procedures, and are approved by the institution's IRB. Each participant in the study will be assigned a study ID number as a unique identifier. All records and research data will be kept in locked filing cabinets and on password-protected, secure computer systems. Databases that link Personal Health Information with research data will be kept on secure, Partners computer systems. Only summaries of group data will be reported in any publications or presentations, with no identification of individual.

IX. REFERENCES

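### The harm stopping rule pairs stopping with disenrollment and does not keep 12- and 24-month outcome follow-up for subjects already randomised

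*Combined protocol and SAP*

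**What the plan says.** Section VIII (Monitoring and Quality Assurance), item 1b, sets out a sequence. Data are reviewed on a running basis. If one arm appears to be doing badly, "further investigation will be initiated to determine if this is an isolated occurrence or if there is a significant trend", and it is such a trend that "warrants cessation of study protocol and disenrollment of subjects". Two rules follow:

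- Rule i: "Stopping rules include a clear difference in morbidity, as measured by interval physical exams and outcomes questionnaires, between treatment groups".
- Rule ii: "Any significant mortality possibly linked to study procedures will result in immediate suspension of the study protocol".

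Under Adverse Events Reporting and Assessment, the same section adds a separate route: "the study may be terminated if the frequency of serious or unexpected adverse events is higher than that anticipated". For suspended studies it says that "an action plan will be devised which will outline what evidence and/or conditions will be required to terminate or re-initiate the study".

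Three other places bear on follow-up:

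- Section III, before the eligibility table: "Our Primary Outcome is change in the modified Harris Hip Score at 12 months and 24 months". The Study Overview places the end of study procedures at the last subject's 24-month follow-up and surveys.
- Section IV, opening paragraph: the surveys are a task for enrolled subjects, and they keep arriving until the subject asks for them to stop.
- Section VIII, Reporting Unanticipated Problems including Adverse Events: problems and adverse events are still reported "after subject withdrawal or completion". Outcome scores are not mentioned.

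**The concern.** Stopping protocol treatment and stopping follow-up are different decisions. Item 1b names both cessation and disenrollment as consequences and does not say that outcome collection continues. If staff apply the rule in its ordinary sense, mHHS collection ends for people who have already had the treatment under suspicion.

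The timing makes this costly. Rule i is judged partly on outcome questionnaires, has no threshold, test or schedule, and is applied under continuous, unblinded review without a monitoring board. A stop reached that way tends to fall when the observed difference is unusually large. Later scores from subjects already randomised are the main protection against an exaggerated final estimate, and they are the data the wording leaves unprotected.

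**Working it through.** **1. What disenrollment adds.** The protocol does not define the word, so the passages have to be read together.

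- Item 1b lists disenrollment next to cessation of the protocol. Cessation already covers stopping protocol treatment, so disenrollment must add something. The natural addition is leaving the study.
- Little else remains to be ended for most subjects. Section IV says the surgery is not a research procedure, and recommended physical therapy sessions run to 12 weeks. After that, what remains of the research is mainly outcome follow-up to 12 and 24 months.
- Section IV assigns the surveys to enrolled subjects. On a plain reading, a disenrolled subject falls outside that duty.
- The post-withdrawal provision in Section VIII covers adverse events and unanticipated problems, not the mHHS.

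On the ordinary meaning, then, the 12- and 24-month mHHS is at risk. Against this, the survey rule in Section IV has only one stated end point, the subject's own request, and makes no exception for a stopped study. The two passages are not reconciled.

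**2. The stopping terms.**

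| Place in Section VIII | Trigger | Consequence named |
|---|---|---|
| Item 1b | Significant trend in one arm, after investigation | Cessation and disenrollment |
| Rule i | Clear difference in morbidity | A stopping rule; consequence not restated |
| Rule ii | Mortality possibly linked to study procedures | Suspension |
| Adverse Events Reporting and Assessment | More serious or unexpected events than anticipated | Possible termination |
| Same place, action plan | Study is suspended | Terminate or re-initiate |

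The action plan matches the suspension in rule ii. The protocol does not say whether a cessation under item 1b counts as a suspension. If it does, evidence for re-initiation might be needed from subjects who have been disenrolled. If it does not, the action plan does not apply to it.

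**3. Size, as illustration.** The stopping rule has no numerical boundary to reproduce.

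Inputs from Section V, Power Analysis: 122 subjects to be enrolled; of 47 past the 2-year mark, 5 were no longer in the study and 11 had not completed surveys.

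Plan's own yield: 47 − 5 − 11 = 31, and 31/47 = 65.96% (printed as 65.95%).

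Assumptions not in the documents: even accrual over A = 4 to 6 years; a stop near full enrolment; surveys ending for everyone at the stop.

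- No 24-month score yet due: 122 × 2/A = 61 (A = 4) to 41 (A = 6), or 50% to 33% of 122.
- Of those, scores that would have been obtained: 61 × 31/47 ≈ 40; 40.7 × 31/47 ≈ 27.
- No 12-month score yet due: 122 × 1/A = 31 (A = 4) to 20 (A = 6), or 25% to 17%.

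The 12-month group is contained in the 24-month group, so the counts must not be added. The 66% is a 2-year yield and is not applied at 12 months. For scale, the plan aims for 70 completers.

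**The case against.** The strongest reply is that one undefined word is being asked to carry too much. No passage says surveys stop. Section IV lets them continue until the subject objects, hopes for several years of outcomes, and allows remote completion. This stands to the extent that the loss is an inference from ordinary meaning. It does not remove the point, because the survey duty is addressed to enrolled subjects and nothing preserves the mHHS after a stop.

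Four stronger readings are tempting, and the documents do not support them:

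- A reader might infer that subjects are disenrolled as soon as harm is suspected. Item 1b puts an investigation first, and disenrollment follows only if a significant trend is found. For the same reason, the trial is not left without any means of checking the signal: a check comes before the stop. What is at risk is later confirmation.
- A reader might infer that item 1b contradicts the re-initiation provision. That provision is written for suspended studies and itself allows termination, whereas item 1b speaks of cessation. Nor does it say that the evidence must be later mHHS scores.
- A reader might infer that treated subjects lose all follow-up. Section IV describes regular clinical follow-up alongside the study's own checks, and adverse-event reporting continues after withdrawal. The research outcome surveys are what is exposed.
- A reader might take 41 to 61 as scores lost. Those are scores not yet due, under an assumed accrual period and a late stop. At the plan's own yield, about 27 to 40 would have been obtained.

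It is also fair to say that this is a contingency that may never arise.

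**Conclusion.** The point holds in a limited form and is worth correcting. As written, item 1b couples stopping with disenrollment and leaves the 12- and 24-month primary outcome of subjects already randomised unprotected if the rule is triggered. This is more than missing detail: a consequence is stated, and following it in its ordinary sense would give a worse result than stopping while continuing follow-up. The loss is nevertheless an inference, since disenrollment is undefined and the survey rule in Section IV points the other way.

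The relation to the suspension, termination and re-initiation wording is an ambiguity to be reconciled.

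On size, roughly 27 to 40 obtainable 24-month scores would be exposed, together with the 12-month scores of 20 to 31 subjects not yet at that visit. These figures rest on even accrual over an assumed 4 to 6 years, a stop near full enrolment, and surveys ending at the stop. The conclusion does not depend on them.

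**What to change.** In Section VIII, item 1b, replace the reference to disenrolling subjects with a statement along these lines: on a stop, new randomisation ceases; subjects already randomised remain in the scheduled mHHS and other outcome surveys to 24 months, sent through the existing REDCap emails and reminder calls, with adverse-event reporting as already described, unless they withdraw consent.

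In the same edit, use cessation, suspension and termination consistently between item 1b, rules i and ii, and Adverse Events Reporting and Assessment, and say which of them the action plan applies to.

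The cost is about one sentence plus the alignment of terms, and some continued survey effort after a stop. No new instrument is needed: the surveys, emails and reminder calls already exist, and no separate adverse-event survey is proposed. The change concerns data collection only. It does not alter when the study stops or what care anyone receives. If the intention was always to continue follow-up, the sentence simply says so.
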